#### **1.4. Compliance**

This study will be conducted in compliance with this protocol, Good Clinical Practice (GCP), and all applicable regulatory requirements.

a subject receiving 3 mg of GS-5829. To minimize the risk of excessive toxicity, the dose escalation of GS-5829 in this protocol will increase at a proportionally smaller percentage at each subsequent dose level.

Assessments for AEs and monitoring for laboratory abnormalities are specified in the protocol and include symptom and AE assessment on Days 1, 8, 15, 22 of the first 28 day cycle and then every 28 days, until end of treatment followed by a 30 day Safety Follow-Up visit. Physical examinations will occur on Day 1 of each 28-day cycle, until end of treatment followed by a 30-day safety follow-up visit.

The safety monitoring frequency is considered sufficient to identify potential AEs as they emerge. In addition, mitigation strategies are incorporated into the study design. The inclusion and exclusion criteria are designed to ensure subjects have acceptable organ function to be eligible for this study such that confounding significant co-morbidities are excluded. Study medications will continue until disease progression, unacceptable toxicity, consent withdrawal, or subject's refusal of treatment.

Enzalutamide is an approved drug for prostate cancer and has known toxicities of seizure, fatigue, back pain, decreased appetite, constipation, arthralgia, diarrhea, hot flushes, upper respiratory tract infection, peripheral edema, dyspnea, musculoskeletal pain, weight decrease, headache, hypertension and dizziness/vertigo. Subjects with a history of seizure will be excluded from receiving enzalutamide.

### **Potential Benefits**

The primary potential benefit of BET inhibition alone or combined with androgen inhibition is that therapy may delay progression or improve overall survival over the current standard of care which is either enzalutamide alone or chemotherapy. Participants are informed that their involvement in the study may offer benefits to other current or future patients with metastatic prostate cancer by enhancing knowledge relating to the disease course and treatment of prostate cancer.

## 2. OBJECTIVES

The primary objectives of this study are as follows:

### Phase 1b Dose Escalation

- To characterize the safety and tolerability of GS-5829 as a single agent and in combination with enzalutamide in subjects with mCRPC
- To determine the maximum tolerated dose (MTD) of GS-5829 as a single agent and in combination with enzalutamide in subjects with mCRPC

### Phase 2 Dose Expansion

- Group 1: To evaluate the efficacy of GS-5829 as a single agent in subjects with mCRPC who have progressed while receiving enzalutamide (may have also received abiraterone) as measured by Progression Rate at Week 24 according to Prostate Cancer Working Group 2 (PCWG2) Criteria
- Group 2: To evaluate the efficacy of GS-5829 combined with enzalutamide in subjects with mCRPC who have progressed while receiving treatment with abiraterone (subjects may not have previously received enzalutamide) as measured by Progression Rate at Week 24 according to PCWG2 Criteria
- Group 3: To evaluate the efficacy of GS-5829 combined with enzalutamide in subjects with mCRPC who have had Prostate-Specific Antigen (PSA) progression, but not radiographic progression, while receiving treatment with enzalutamide (may have also previously received abiraterone), as measured by Progression Rate at Week 24 according to PCWG2 Criteria

The secondary objectives of this study are as follows:

### Phase 1b Dose Escalation

- To evaluate the pharmacokinetics (PK) of GS-5829 as a single agent and in combination with enzalutamide in subjects with mCRPC
- To evaluate the efficacy of GS-5829 as a single agent and in combination with enzalutamide in subjects with mCRPC as measured by PCWG2 Criteria

## Phase 2 Dose Expansion

- To evaluate the safety and tolerability of GS-5829 as a single agent and in combination with enzalutamide in subjects with mCRPC
- Group 1: To evaluate the efficacy of GS-5829 in subjects with mCRPC who have progressed while receiving abiraterone as measured by prostate specific antigen (PSA) at Week 12, progression-free survival (PFS) and overall survival (OS)
- Group 2: To evaluate the efficacy of GS-5829 combined with enzalutamide in subjects with mCRPC who have progressed while receiving abiraterone as measured by PSA at Week 12, PFS and OS
- Group 3: To evaluate the efficacy of GS-5829 combined with enzalutamide in subjects with mCRPC who have had PSA progression, but not radiographic progression, while receiving enzalutamide, as measured by PSA at Week 12, PFS and OS

The exploratory objectives of this study are as follows:

■

## 3. STUDY DESIGN

### 3.1. Endpoints

The endpoints for this study are described in Section 8.

### 3.2. Study Design

**Phase 1b Dose Escalation:** This is an open-label, multicenter, sequential dose-escalation study to evaluate the safety, tolerability, PK, and PD of GS-5829 as a single agent and in combination with enzalutamide in subjects with mCRPC.

#### Dose Escalation of GS-5829

Subjects with mCRPC who have progressed on either abiraterone and/or enzalutamide will be sequentially enrolled at progressively higher dose levels to receive oral GS-5829 as single agent once daily. Dose escalation [3+3] will be performed with cohort sizes of 3 to 6 subjects. Initially 3-4 subjects will be enrolled into each dose level. The study will be initiated at a dose level that has been demonstrated to be safe and tolerable in the ongoing Phase 1 study (GS-US-350-1599) in patients with solid tumors and lymphomas. Subjects will return to the clinic for frequent evaluation and monitoring as per the Study Procedures Table found in [Appendix 2](#) and [Appendix 3](#).

The doses for each monotherapy dose level are shown in the table below.

**Table 3-1. Dose Escalation**

Dose Level	GS -5829 (once daily)
1*	1.4 mg
2	2 mg
3	3 mg
4	4 mg
5	6mg
6	9 mg

\* The initial dose level may be higher than dose level 1, depending on results in Study GS-US-350-1599

Dose levels may be modified based on emerging safety, PK, PD, and efficacy results.

If a DLT occurs within 28 days at the first dose level, this level will be expanded to enroll 2-3 additional subjects (6 subjects total). If  $\geq 2$  DLTs occur in the first dose level tested, then one dose level lower will be opened to enroll 3-4 additional subjects. If no DLT occurs in 3-4 subjects or  $< 2$  DLTs occur in up to 6 subjects at the lower dose level, then this dose level will be the MTD of single agent GS-5829.

The safety and tolerability of each dose level will be assessed by a Safety Review Team (SRT) after all subjects in the cohort have been followed for at least 28 days after the first dose of GS-5829. If no DLTs occur in 3-4 subjects or < 2 DLTs occur in up to 6 subjects on the first dose level after 28 days on treatment, the second cohort will open. Each subsequent cohort will open if the dose level preceding has no DLTs in 3-4 subjects or < 2 DLTs in up to 6 subjects.

The SRT will consist of at least one investigator and the following:

Gilead Sciences, Inc. (Gilead) study team members: the Medical Monitor, representatives from Drug Safety and Public Health (DSPH), Clinical Operations and Biostatistics. Others may be invited to participate as members of the SRT if additional expertise is desired. The Medical Monitor serves as the chair of the SRT.

If a subject is enrolled in a cohort but does not complete the PK or PD analysis in the first 28 days of dosing, they may continue on study but an additional subject may be enrolled at that dose level.

The MTD of monotherapy is the highest dose level with a subject incidence of 0 DLTs in 3-4 subjects or < 2 DLTs in 6 subjects during the first 28 days of study drug dosing. A minimum of 3 subjects need to be treated in a cohort before this dose level is deemed as the MTD. If we do not determine the MTD of single agent GS-5829, the dose selected for expansion phase will be the highest administered monotherapy dose. If the lowest dose evaluated is deemed the MTD, then the lower dose cohort may be enrolled to explore the relationship between exposure and efficacy and safety.

The combination dose escalation may initiate prior to identification of the MTD of single agent GS-5829 using a starting dose of GS-5829 that has been determined to be safe and tolerable in the single agent dose escalation.

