### **Dose Escalation of GS-5829 and enzalutamide**

The first 3-4 subjects to enroll will receive GS-5829 at a dose level less than or equal to the previously determined MTD (or a monotherapy dose that has been determined to be safe), combined with enzalutamide. Enzalutamide is a strong CYP3A4 inducer, which is expected to decrease the exposure of GS-5829 and therefore a higher dose of GS-5829 may be required to achieve target coverage compared to the single agent dose. Subjects will administer enzalutamide 160 mg once daily as a single agent starting on Study Day 1 through Cycle 1 Day 1. On Cycle 1 Day 1 (approximately 14 days after Study Day 1), subjects will administer GS-5829 once daily in combination with enzalutamide 160 mg once daily in order to evaluate the interaction of the 2 agents. Depending on the observed PK interaction, toxicity and tolerability observed in the single agent dose escalation, the dose escalation may continue beyond a dose which has been identified to be safe and tolerable in the single agent arm. Any increase in the dose of GS-5829 will not be more than 100% in the next cohort.

Similar to the single agent dose escalation, the available safety, tolerability and PK data for each combination therapy cohort will be assessed by an SRT after all subjects in the cohort have been followed for at least 28 days after the first dose of GS-5829. If no DLTs occur in 3-4 subjects or

< 2 DLTs occur in up to 6 subjects on the first dose level after 28 days on treatment (C1D28), the second dose level will open. Each subsequent dose level will open if the dose level preceding has no DLTs in 3-4 subjects or < 2 DLTs in up to 6 subjects. The dose escalation intended is similar to that of the single agent GS-5829 (see [Table 3-1](#)). Depending on the exposure observed, the data (including PK, tolerability, safety and PSA response) will be evaluated to determine the appropriate GS-5829 dose in combination with enzalutamide. The dose of GS-5829 for the next combination therapy cohort will be communicated to the sites by administrative letter.

If a subject is enrolled in a cohort but does not complete the PK or PD analysis in the first 28 days of GS-5829 dosing, they may continue on study but an additional subject may be enrolled at that dose level.

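### The escalation rule accepts fewer than 2 DLTs in *up to 6* subjects while the MTD definition requires 6, and expansion after a DLT is written only for the first monotherapy level (minor wording fault)

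*Protocol*

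**What the plan says.** The monotherapy text in Protocol Section 3.2 describes the design this way: "Dose escalation [3+3] will be performed with cohort sizes of 3 to 6 subjects". Each level starts with 3-4 subjects.

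- **Opening the next monotherapy level:** "Each subsequent cohort will open if the dose level preceding has no DLTs in 3-4 subjects or < 2 DLTs in up to 6".
- **Opening the next combination level:** for the first level, no DLTs in 3-4 subjects or fewer than 2 in the larger group, worded "DLTs occur in up to 6 subjects on the first dose level after 28 days on treatment (C1D28), the second dose level will open". For later levels: "Each subsequent dose level will open if the dose level preceding has no DLTs in 3-4 subjects or < 2 DLTs in up to 6".
- **General MTD definition:** the highest level at which there is "a subject incidence of 0 DLTs in 3-4 subjects or < 2 DLTs in 6 subjects during the first 28 days". The combination definition uses the same counts.
- **Expansion after a DLT:** "If a DLT occurs within 28 days at the first dose level, this level will be expanded to enroll 2-3 additional subjects", for 6 in total. This sentence stands only in the monotherapy text and only for the first level.
- **Lower-dose fallback:** if the first monotherapy level has 2 or more DLTs, one level lower is opened. That level becomes the MTD on no DLTs in 3-4, or on fewer than 2 in the larger group, worded "DLTs occur in up to 6 subjects at the lower dose level, then this dose level will be the MTD of single agent GS-5829".
- **Minimum for the MTD:** "A minimum of 3 subjects need to be treated in a cohort before this dose level is deemed as the MTD".

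The synopsis repeats the escalation, fallback and MTD rules with the same denominators. SAP Section 1.2 also calls the combination escalation a 3+3 design, but gives no decision rule.

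**The concern.** In a 3+3 design, one DLT among the first 3 subjects leads to more subjects at the same dose before anyone is treated higher. Here that step is spelled out once, for the first monotherapy level. Elsewhere the opening criterion can be met by 1 DLT in 3, 4 or 5 subjects, because each of those is fewer than 2 in up to 6. The fallback has a related fault: it can declare an MTD on a count that the general definition in the same section rejects.

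This is a safety rule, and finding the MTD is a primary objective of phase 1b. A single early DLT was foreseeable. Protocol Section 1.3.1 refers to a narrow therapeutic index in dogs. Section 1.2.3 reports a DLT in 1 of 6 subjects at 3 mg in the companion study, and Section 1.5 reports another at 4 mg. Both doses are planned levels here. In the combination part a step may be as large as 100%.

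**Working it through.** **Step 1: the two rules side by side.** This applies to any monotherapy level after the first and to any combination level.

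| DLTs at the level | Next level opens, literal reading | Level meets the general MTD definition |
|---|---|---|
| 0 in 3-4 | yes | yes |
| 1 in 3, 4 or 5 | yes | no |
| 1 in 6 | yes | yes |
| 2 or more | no | no |

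The rules disagree in the second row only. At the first monotherapy level that row cannot be final, because expansion to 6 is mandatory there.

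**Step 2: the plan's own figure.** The only number tied to the escalation rule is the phase 1b maximum of 72 (Protocol Section 4.1). Table 3-1 has 6 levels and there are two escalations, so 6 levels x 2 escalations x 6 subjects = 72. The documents do not show this derivation; it is inferred. It fits an intent to allow 6 subjects at every level.

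**Step 3: chance of clearing one level.** Let p be the true DLT rate. The documents give no rate for these levels, so p is assumed over a range.

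Start with 3 subjects:
- Literal: P(0/3) + P(1/3) = (1-p)^3 + 3p(1-p)^2
- 3+3: P(0/3) + P(1/3) x P(0/3)

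Start with 4 subjects, 2 added after a DLT:
- Literal: P(0/4) + P(1/4) = (1-p)^4 + 4p(1-p)^3
- 4+2: P(0/4) + P(1/4) x P(0/2)

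Worked at p = 0.10:
- Start 3: literal 0.729 + 0.243 = 0.972; 3+3 gives 0.729 + 0.243 x 0.729 = 0.906; gap 0.066.
- Start 4: literal 0.6561 + 0.2916 = 0.948; 4+2 gives 0.6561 + 0.2916 x 0.81 = 0.892; gap 0.055.

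| Assumed p | Start 3: literal | Start 3: 3+3 | Gap | Start 4: literal | Start 4: 4+2 | Gap |
|---|---|---|---|---|---|---|
| 0.10 | 0.972 | 0.906 | 0.066 | 0.948 | 0.892 | 0.055 |
| 0.20 | 0.896 | 0.709 | 0.187 | 0.819 | 0.672 | 0.147 |
| 0.33 | 0.745 | 0.434 | 0.311 | 0.599 | 0.380 | 0.219 |
| 0.50 | 0.500 | 0.172 | 0.328 | 0.313 | 0.125 | 0.188 |

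Gaps are taken before rounding. They ignore any intervention by the Safety Review Team and do not apply to the first monotherapy level.

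**The case against.** The best reply is that nobody would read the rule literally. The same *up to 6* wording is used for the first monotherapy level, where expansion is mandatory, so there it must mean the expanded cohort. The next sentence carries the criterion forward to later cohorts. If *up to 6* already covered 3-4 subjects, the separate limb for no DLTs in 3-4 would be redundant. Both escalations carry the 3+3 label. The Safety Review Team assesses every cohort. In the combination part, PK, tolerability, safety and PSA response are weighed before a dose is chosen and sent to sites by administrative letter. Finally, SAP Section 1 says that the study stopped during escalation and that all phase 1b subjects are off drug, so rewording changes no dosing decision.

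Most of this stands, and it is why the point is minor. It settles the intent but does not supply the rule: no sentence requires expansion at the other levels, and team review does not oblige anyone to add subjects. In the combination text, the references to similarity with the single-agent part cover the review and the dose steps, not expansion.

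A reader might go further and infer that levels were opened after 1 DLT in 3-4 subjects, or that patients were put at risk. The documents do not support that: none reports such a decision. The fallback was probably never used either. The SAP lists monotherapy doses from 2 mg, and Protocol Section 1.5 reports 2 mg as safe and tolerable in this study.

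**Conclusion.** The rule is wrong as written, with minor severity. The escalation criterion and the monotherapy fallback use a different denominator from the general MTD definitions, and the expansion step is missing for every level except the first monotherapy one. Ordinary 3+3 is the evident intent.

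The gaps of 5.5-6.6 percentage points at a 10% DLT rate and 22-31 points at 33% show what the literal wording would allow. They rest on assumed DLT rates, independent subjects and no intervention by the Safety Review Team. They should not be read as an estimate of risk in this trial, because they model a reading that was probably not intended.

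What remains open is reporting. The SAP states no rule of its own for deriving the MTD and plans a listing of DLTs (Section 7.1.7.1). With two denominators in the protocol, a reader of the report could not tell which one decided each level.

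**What to change.** **Wording, in the synopsis and Section 3.2, for every level of both escalations:**
1. One DLT in the initial 3-4 subjects requires expansion to 6 DLT-evaluable subjects before any escalation.
2. Replace *up to 6* with 6 in the escalation criterion and in the monotherapy lower-dose fallback.

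A level with no DLTs in 3-4 subjects still needs no expansion, and the minimum of 3 for the MTD stands.

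**Cost of the wording:** 2-3 more subjects at a level with one DLT. The documents do not show that this always fits the planned 72. The inferred 6 x 2 x 6 uses the whole number and leaves nothing for replacements (Section 6.11), extra subjects for incomplete PK or PD (Section 3.2), or added combination cohorts (Section 1.3.1).

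**For this trial, with dosing over:** apply the denominator of 6 throughout. This mostly restates the general MTD definition; the change is that it also governs the fallback. Report DLTs over DLT-evaluable subjects by dose level, and flag any level passed on 1 DLT in fewer than 6. The cost is one table. Its inputs are already planned: the DLT Analysis Set (SAP Section 3.1.4), set counts by treatment group (Section 3.1) and the DLT listing.

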### Figure 3-1. Study Design and Treatment Schema

### Phase 2 – DOSE EXPANSION

- Dose expansion will begin after completion of the corresponding dose-escalation phase treatment
  - Group 1: GS-5829
  - Group 2: GS-5829 + enzalutamide
  - Group 3: GS-5829 + enzalutamide
- Dose level based upon results from the dose-escalation phase
- Up to 20 additional subjects in each arm

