## **6.11.          Replacement of Subjects**

If a subject is withdrawn from the study for any reason other than a DLT prior to completion of the DLT assessment window, a replacement subject will be enrolled at the same dose level as the replaced subject. To be evaluable for the DLT observation, a subject must receive at least 21 doses of GS-5829, complete all safety procedures through Day 28, or experience a DLT prior to Day 28.

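### When no single-agent MTD is determined, the expansion dose defaults to the highest level administered rather than the highest level cleared, and the protocol does not say when an MTD counts as not determined

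*Protocol*

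**What the plan says.** All the monotherapy rules are in Protocol Section 3.2, Dose Escalation of GS-5829.

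- **Design:** "Dose escalation [3+3] will be performed with cohort sizes of 3 to 6 subjects".
- **Expansion of a cohort after one DLT:** "If a DLT occurs within 28 days at the first dose level, this level will be expanded to enroll 2-3 additional subjects". This is written for the first level only. At higher levels it rests on the 3+3 label.
- **Review:** each level "will be assessed by a Safety Review Team (SRT) after all subjects in the cohort have been followed for at least 28 days".
- **Opening the next level:** allowed when "the dose level preceding has no DLTs in 3-4 subjects or < 2 DLTs in up to 6 subjects".
- **MTD:** "the highest dose level with a subject incidence of 0 DLTs in 3-4 subjects or < 2 DLTs in 6 subjects", with at least 3 subjects treated.
- **Fallback:** "If we do not determine the MTD of single agent GS-5829, the dose selected for expansion phase will be the highest administered monotherapy dose".

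The Phase 2 part of Section 3.2 sets the Group 1 dose at or below the monotherapy MTD, for approximately 20 subjects, and allows enrolment once that MTD has been identified. Figure 3-1 adds: "Dose expansion will begin after completion of the corresponding dose-escalation phase treatment". The protocol synopsis and SAP Section 1.2 do not repeat the fallback.

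**The concern.** The fallback is mandatory and has one condition, that no MTD was determined. It names the highest dose *administered*. A level can have been administered without being cleared: its cohort may be incomplete, it may stand at 1 DLT in 3 subjects, or it may have failed. Nothing in the sentence excludes such a level.

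The stake is the dose given to about 20 Group 1 subjects. The protocol gives its own reasons to care about a single step. Section 1.3.1 cites a narrow therapeutic index in dogs, with an exposure margin of about 1-fold at the highest non-severely toxic dose. Section 1.5 reports adrenal hemorrhage as a DLT at 4 mg in the first-in-human study.

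**Working it through.** The plan gives no figure to reproduce here. The check applies the Section 3.2 rules to example outcomes under two readings of when an MTD is determined.

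**Definitions.** *Cleared* means meeting the counts in the MTD definition: 0 DLTs in 3-4 subjects, or fewer than 2 in 6.

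- *Literal reading:* the MTD is the highest cleared level. No higher level needs to have failed.
- *Bracketed reading:* an MTD exists only once a higher level has had 2 or more DLTs.

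**Support in the text.** The definition itself is literal. Other wording in Section 3.2 treats a cleared dose and an identified MTD as different things. Combination dosing may start before the MTD is identified, at a dose already found safe. The combination starting dose is tied either to the MTD or, as an alternative, to a monotherapy dose found safe. Combination escalation may also stop before the MTD is reached. These passages favour the bracketed reading without settling it.

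**Outcomes** (DLTs/subjects; hypothetical data):

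| Situation | Literal reading | Bracketed reading |
|---|---|---|
| All levels cleared up to 9 mg | MTD 9 mg | No MTD; fallback gives 9 mg, cleared |
| 4 mg cleared, 6 mg at 2/4 | MTD 4 mg | MTD 4 mg |
| 4 mg cleared, 6 mg at 0/2 or 1/3 | MTD 4 mg; fallback not reached | No MTD; fallback gives 6 mg, uncleared |
| First level 2 mg, stopped at 0/2 | No MTD; fallback gives 2 mg, uncleared | Same |
| 2 mg at 2/3, then 1.4 mg at 2/3 | No MTD; fallback gives 2 mg, failed | Same |

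The first two rows show no problem on either reading. The third depends on the reading. The last two go wrong on both, but no cleared level is passed over there because none exists.

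**Size of one step** (ratios of adjacent doses in Table 3-1):

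- 2/1.4 = 1.43, or +43%
- 3/2 = 1.50, or +50%
- 4/3 = 1.33, or +33%
- 6/4 = 1.50, or +50%
- 9/6 = 1.50, or +50%

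The range is 33% to 50%, and it is the same from 2 mg upward, the levels listed in SAP Section 1.2. This is the excess in the third situation only. The documents give no basis for the probability that escalation stops with an unfinished cohort, so none is estimated.

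**With the fix**, the first situation still allows up to 9 mg, the second and third allow no more than 4 mg on either reading, and in the last two Group 1 does not open.

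**The case against.** The strongest reply is that the MTD definition stands just before the fallback and requires no failed higher level. With 4 mg cleared and 6 mg unfinished, 4 mg is then the MTD and the fallback is never reached. A reader might infer that the protocol plainly sends Group 1 to an unfinished level over the cleared one below. The documents do not support that as a certainty, since it needs the bracketed reading. This part of the objection stands.

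The Group 1 text also limits the dose to the MTD and ties enrolment to an identified MTD, so without one there may be no trigger to open the group. But those lines presuppose an MTD. The fallback is the sentence written for its absence, and the protocol does not reconcile the two.

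Other controls make the path less likely. The Safety Review Team assesses every level. Figure 3-1 puts expansion after completion of escalation and bases its dose level on the escalation results. Under Section 6.11, when a subject withdraws before the end of the DLT window for a reason other than a DLT, "a replacement subject will be enrolled at the same dose level as the replaced subject". The express option to stop before the MTD is written only for the combination. All of this stands, but none of it requires that the dose named by the fallback was cleared.

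Finally, Section 1.5 reports that 2 mg had been found safe and tolerable in this study by 17 June 2016. If that means 2 mg met the DLT criterion, the fallback could no longer apply on the literal reading. Section 1.5 gives no cohort counts. It also does not call 2 mg the MTD, which again fits the bracketed usage.

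**Conclusion.** The point holds as a minor design-stage safety correction. The fallback should refer to a cleared dose, and the protocol leaves open when the MTD counts as not determined. On the literal definition the fallback names an uncleared or failed dose only when no level has cleared. On the bracketed reading it can also choose an unfinished top level, 33% to 50% above the cleared level below, for about 20 subjects. That second result rests on the bracketed reading and on monotherapy escalation stopping with its last cohort unfinished.

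A reader might also infer that subjects were treated at an uncleared expansion dose. They were not: the SAP Introduction says the sponsor ended the study during escalation without moving to Phase 2.

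**What to change.** Replace the fallback sentence in Protocol Section 3.2 with:

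> If no single-agent MTD has been determined, the expansion dose will not exceed the highest monotherapy level that met the DLT criterion (0 DLTs in 3-4, or < 2 in 6, DLT-evaluable subjects over 28 days) and was reviewed by the SRT. If no level qualifies, Group 1 will not open.

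This works on either reading of the MTD. It sets only a ceiling, so the choice of dose at or below it stays with the sponsor and the Safety Review Team. It uses the counts already in the MTD definition, so neither that definition nor the escalation rule needs to change. The cost is one sentence, with no added subjects, visits or procedures.
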